Research Protocol

NCT: Not Assigned Yet

Document Date: 01/08/2023

Following approval from the institutional ethics committee, adult patients undergoing cholecystectomies, appendectomies, and urgent intestinal obstruction surgeries will be enrolled. Patients under the age of 18, pregnant individuals, those with a history of bariatric surgery, esophageal pathology, or non-acute mechanical gastric emptying obstruction will be excluded. Informed consent will be obtained. Prior to anesthesia induction, gastric content will be assessed by an experienced operator. A Sonosite Edge II ultrasound system with a low-frequency convex transducer (2-5 MHz) will be used for this purpose. Standardized ultrasound windows, as described in previous studies (Van de Putte, et al), will be obtained. The patient will be placed in the dorsal decubitus position to visualize the gastric antrum, aorta, superior mesenteric artery, inferior vena cava, liver, and pancreas. If solid or thick liquid gastric content is observed, patients will be immediately classified as having a full stomach. If no content is visualized or clear liquid is evident, the patient will be placed in the right lateral decubitus position. A scan will be performed from the left subcostal border to the right, sequentially visualizing the body, antrum, and pylorus. The characteristic 5-layered structure of the gastric wall will be identified: hyperechoic serosa, hypoechoic muscularis propria, hyperechoic submucosa, hypoechoic muscularis mucosa, and hyperechoic air-mucosa interface. If clear liquids are visualized, the volume will be quantified using the formula derived from the study by Perlas, et al (2013), which considers the cross-sectional area in the right dorsal decubitus position and the patient's age:
$$\text{Vol (mL)} = 27.0 + 14.6 \times \text{CSA (cm}^2) - 1.28 \times \text{age (years)}$$
*CSA: cross-sectional area. Volumes greater than 1.5 mL/kg will be considered as a full stomach. In cases of procedure intolerance due to discomfort or non-cooperation, the examination will be terminated, and the patient will be excluded from the study. Patient demographic data, surgical pathology and severity, comorbidities, fasting hours, measured gastric content, type of anesthesia, qSOFA score, and occurrence of adverse events such as desaturation, regurgitation, or aspiration will be recorded anonymously. The sample size calculation used the method for estimating a proportion. A prevalence of 17% based on previous pilot studies(9), with a confidence interval of 5% and a confidence level of 95%, resulted in a total of 217 patients to be recruited. Accounting for a 10% loss, a final total of 242 patients will be included. Continuous data will be presented as mean \pm standard deviation or median and interquartile range, as appropriate. Group comparisons will be performed using Student's t-test for independent samples or the Mann-Whitney U-test, depending on the distribution. Categorical data will be presented as absolute counts and corresponding percentages. Differences will be analyzed using Fisher's exact test or the Chi-square test. For association analysis, univariate and multivariate linear or logistic regressions will be conducted, as appropriate. A significance level of 0.05 will be considered, along with a corresponding 95% confidence interval. All calculations will be performed using statistical software.

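### Does a volume in mL that exists only for clear-liquid stomachs undermine the planned association analyses?

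*Combined protocol and SAP*

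**What the plan says.** Everything relevant is in the unnumbered Research Protocol of the combined document.

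The scan rules create three branches. For the first: "If solid or thick liquid gastric content is observed, patients will be immediately classified as having a full stomach". For the other two: "If no content is visualized or clear liquid is evident, the patient will be placed in the right lateral decubitus position". The formula then applies to one of those two: "If clear liquids are visualized, the volume will be quantified using the formula derived from the study". The cut-off follows: "Volumes greater than 1.5 mL/kg will be considered as a full stomach".

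The list of recorded data includes "fasting hours, measured gastric content, type of anesthesia, qSOFA score", with no restriction to one branch.

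The statistical text gives methods without naming outcomes. "Group comparisons will be performed using Student's t-test for independent samples or the Mann-Whitney U-test, depending on the distribution". For associations, "univariate and multivariate linear or logistic regressions will be conducted, as appropriate". The sample size is calculated for a single proportion and nothing else.

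**The concern.** Volume is the only continuous gastric measure that the plan derives, so it is the natural candidate if someone fits a linear regression. Yet whether a patient has a volume depends on the gastric content itself. Solid or thick stomachs, which the protocol regards as full, have none. Empty stomachs have no stated value, not even zero. An analysis of mL in whoever has a number would lose both ends of the distribution, and covariate adjustment does not undo selection on the outcome.

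At stake is an association estimate that could be shrunk, unaffected or even reversed, and that could contradict the full-stomach result in the same report. The formula also has no floor: it returns negative volumes for small areas in older patients, so applying it to empty stomachs would not fill the gap by itself.

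**Working it through.** **1. What the study is sized for.** Inputs from the sample-size text: p = 0.17, margin 0.05 read as a half-width, 95% confidence.

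n = 1.96² × 0.17 × 0.83 / 0.05² = 216.8, rounded up to 217. With 10% loss, 217 / 0.9 = 241.1, rounded up to 242. Both stated figures reproduce. They concern the proportion with a full stomach, about 0.17 × 217 = 36.9 patients.

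**2. Which outcomes exist in which branch.**

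| Branch | mL | Full / not full |
|---|---|---|
| Solid or thick | none | full, by type of content |
| Clear liquid | from the formula | by 1.5 mL/kg |
| No content | not stated | not full, by implication |

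The binary class is available in all three branches, so the prevalence estimate and the chi-square, Fisher and logistic analyses of that class are untouched.

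**3. How bad an mL analysis could be.** The documents give no shares of empty, clear and solid stomachs. Five sets are assumed, each with 17% full. Content is one normal scale z = 0.30x + √(1 − 0.30²)e, cut at the cumulative shares, with N = 217 and two-sided 0.05. Two versions of the linear regression are compared with logistic regression on full versus not full in all 217. One version uses clear-liquid patients only. The other keeps empty stomachs at the floor value and omits only solid or thick content.

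| Empty / clear low / clear high / solid (%) | Clear-only n | Clear-only slope | Clear-only power | Power, empties at floor | Logistic power |
|---|---|---|---|---|---|
| 43/40/7/10 | 102 | 0.051 | 23% | 85% | 87% |
| 30/53/12/5 | 141 | 0.100 | 53% | 97% | 89% |
| 60/23/7/10 | 65 | 0.026 | 12% | 76% | 86% |
| 20/63/2/15 | 141 | 0.080 | 44% | 88% | 86% |
| 10/73/12/5 | 184 | 0.168 | 88% | 98% | 88% |

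The clear-only and logistic columns use 600 simulated datasets per set (Monte Carlo error up to about 2 points); the floor column uses 1,500. A repeat run gave 10% to 88% for clear-only power and 72% to 97% with empties at the floor. As fractions of the true slope, the clear-only estimates run from 0.026/0.30 = 9% to 0.168/0.30 = 56%. Keeping the empties restores most of the power but not the full slope: the lower end is flattened and solid stomachs are still missing. If omission is unrelated to volume, there is no attenuation (mean slope 0.303 against 0.30).

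**4. Reversal.** Suppose a factor moves empty/clear/solid from 60/35/5 to 25/60/15 and mean clear volume from 60 to 50 mL. The clear-only difference is 50 − 60 = −10 mL. Among non-solid patients with empties at 0 mL it is (0.60/0.85) × 50 − (0.35/0.95) × 60 = 35.3 − 22.1 = +13.2 mL. These answer different questions. The second also leaves out 5% and 15% of patients respectively, so it is not an unselected benchmark.

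**5. Negative volumes.** The formula gives zero at area (1.28 × age − 27)/14.6, which is 3.41 cm² at age 60 and 5.16 cm² at age 80. At 3 cm² and age 75 it gives 27 + 43.8 − 96 = −25.2 mL. Any negative value is below 1.5 mL/kg, so the patient remains not full.

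**The case for a change.** The best case for acting is that the statistical text leaves the choice between linear and logistic regression open until the data are in, and that one sentence would close it. Nothing in the document says how empty or solid stomachs would enter an analysis of mL. If an author regressed volume on, say, fasting hours in the clear-liquid group and reported the result as applying to all patients, the estimate would be selected on content and the criticism would be fair. All of that stands.

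It does not show that the plan calls for such an analysis. The t-test and Mann-Whitney wording fits a comparison of age or fasting hours between full and not-full patients. Patients with no visible content go on to the same right-lateral scan as those with clear liquid, and reading their volume as 0 mL is natural, though unstated.

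Nor is there a clearly better replacement. A four-level ordinal model (empty, clear liquid up to the cut-off, clear liquid above it, solid or thick) ranks solid content above high-volume clear liquid. The protocol gives no such order: both are simply full. The single scale in the simulation favours that model by construction. A two-part model whose second part uses only patients with content conditions on content again. Reasonable statisticians would differ on all of these.

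**Conclusion.** No change to the plan follows. Volume is missing by design outside the clear-liquid branch, but the quantity that the study is built to estimate does not depend on having a volume for everyone. The sample size, the prevalence estimate and the comparisons of full with not full are unaffected, and logistic regression on that class in all scanned patients is already permitted.

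The potential harm is conditional on an analysis that the plan does not name. Its size rests on assumed shares, an assumed slope and a single latent scale that places solid content at the top, and its direction is not fixed. What is left is missing detail about the regression outcome. A competent analyst would take full versus not full as that outcome and describe mL within the clear-liquid group. The conclusion assumes that patients with no visible content are counted as not full, which the rules imply without saying so. It would not excuse a report that presented a clear-liquid-only regression on mL as a result for all patients.

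### Does the undefined body position in the gastric-volume formula sentence leave the full-stomach classification open?

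*Combined protocol and SAP*

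**What the plan says.** All the relevant text is in the unnumbered Research Protocol of the combined protocol and SAP, in this order:

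- **First look.** "The patient will be placed in the dorsal decubitus position to visualize the gastric antrum", along with neighbouring landmarks.
- **Branch that never reaches the formula.** "If solid or thick liquid gastric content is observed, patients will be immediately classified as having a full stomach".
- **Branch that continues.** "If no content is visualized or clear liquid is evident, the patient will be placed in the right lateral decubitus position".
- **Second scan.** The operator sweeps across the upper abdomen, "sequentially visualizing the body, antrum, and pylorus".
- **Formula step.** "If clear liquids are visualized, the volume will be quantified using the formula" taken from a named 2013 study, "which considers the cross-sectional area in the right dorsal decubitus position" together with age. The equation follows: volume in mL = 27.0 + 14.6 × CSA (cm²) − 1.28 × age (years).
- **Classification.** After the equation, the text only expands the abbreviation CSA and sets the cut-off: "Volumes greater than 1.5 mL/kg will be considered as a full stomach".

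**The concern.** The position named in the formula sentence occurs once, is not defined, and matches neither scan position. It joins *right* from one to *dorsal* from the other. The antrum is imaged in both positions, so an area could physically be traced in either. No separate sentence settles the matter.

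CSA is the only ultrasound measurement in the equation; the other input is age. In patients with clear liquid the calculated volume alone decides the class. The study is sized to estimate a proportion, and full stomach is the only classification the protocol defines, so the natural inference is that this class is what the 17% refers to. If different operators entered areas from different positions, some patients near the cut-off could be classed differently, and a reader could not tell from the text which rule had been used.

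**Working it through.** **1. The plan's own figure.** Inputs from the sample-size sentences: prevalence p = 0.17, precision d = 0.05 taken as a half-width, 95% confidence (z = 1.96), 10% loss.

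- n = z² × p(1 − p) / d² = 3.84 × 0.17 × 0.83 / 0.0025 = 216.8, rounded up to 217.
- 217 / 0.90 = 241.1, rounded up to 242.

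Both match the protocol. Neither uses CSA or body position.

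**2. Where the patient lies when the formula is applied.**

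| Finding in dorsal decubitus | Next step in the protocol | Position when the formula step is reached |
|---|---|---|
| Solid or thick liquid | Classified at once | Formula not used |
| Clear liquid | Turned and rescanned | Right lateral |
| Nothing seen | Turned and rescanned | Right lateral, if liquid then appears |

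Every route to the formula passes through the right lateral scan. Two details support reading the odd term as right lateral:

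- In the third row, liquid can first be seen only after the turn. A dorsal area would come from an antrum in which the operator saw no content, so a dorsal reading fits that row badly.
- Right lateral is the only position in the procedure whose name contains *right*.

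No sentence instructs the operator to enter an area from the first position. There is one mis-worded label, not two competing rules.

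**3. How sensitive the class is to CSA.** The coefficient and cut-off come from the protocol. Weights and ages are assumptions.

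- Change in volume per 1 cm²: 14.6 mL. Per kg: 14.6/50 = 0.29, 14.6/70 = 0.21 and 14.6/100 = 0.15 mL/kg.
- As a share of the cut-off volume (1.5 × weight): 14.6/75 = 19.5%, 14.6/105 = 13.9% and 14.6/150 = 9.7%.
- CSA at the cut-off = (1.5 × weight − 27.0 + 1.28 × age) / 14.6. At age 40 and 50, 70 and 100 kg:
  - (75 − 27 + 51.2)/14.6 = 6.79 cm²
  - (105 − 27 + 51.2)/14.6 = 8.85 cm²
  - (150 − 27 + 51.2)/14.6 = 11.93 cm²
- Example at age 50 and 70 kg:
  - CSA 9 gives 27 + 131.4 − 64 = 94.4 mL, or 94.4/70 = 1.35 mL/kg (not full).
  - CSA 10 gives 27 + 146 − 64 = 109.0 mL, or 109.0/70 = 1.56 mL/kg (full).

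**4. What these numbers do and do not show.** They describe how the class responds to any error in CSA, whatever its cause. Replace the odd term with right lateral and every figure in step 3 stays the same. To turn the wording into a shift in prevalence one would need the CSA difference between positions, the share of patients with clear liquid, and evidence that dorsal areas would be entered. The documents supply none of these.

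**The case for a change.** The best case for acting is that a rule feeding the main classification should be explicit, and this one is not. The right lateral reading is an inference from step order. *Dorsal* is the name of the first position, the antrum is visible there too, and neither the experienced operator nor the standardised windows says which area enters this particular equation. A 1 cm² discrepancy can move a patient across the cut-off, and the correction would take one sentence.

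Much of that stands as a comment on drafting: the term is wrong as written, and no other sentence states the position outright. The step to an unreliable outcome does not follow. The order of the scan leads to one position on every route to the formula. The protocol also prints the full equation and names the study it comes from, so investigators and anyone repeating the work can confirm the required position there. The sensitivity figures cannot carry the argument, because they are not caused by the wording. A low cost of correction is a reason to tidy a sentence; it does not show that the plan would otherwise give a different result.

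**Conclusion.** This is a clerical slip in naming a body position. The surrounding procedure resolves it, and no change to the plan follows. Correcting the word would alter no scan step, classification rule, sample size or analysis. Patients with solid or thick content are outside its reach altogether, and 217 and 242 are unaffected. The effect on prevalence that can be shown from the documents is nil; the 0.15 to 0.29 mL/kg per cm² (at assumed weights of 100 down to 50 kg) is a property of the formula.

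The conclusion rests on one assumption: that operators follow the written order and measure the area in the position the patient then occupies. It would need revisiting only if there were evidence that areas from the first, dorsal scan were being entered into the equation. The documents contain none.

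### Student's t-test is planned with no provision for unequal variances; at the likely 37 vs 180 split, an assumed 1.5-fold SD difference moves its 5% error to about 1% or 13%

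*Combined protocol and SAP*

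**What the plan says.** The Research Protocol has no numbered sections; the relevant text is its sample size and statistical analysis paragraph.

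- **Group comparisons.** Continuous data are compared with Student's "t-test for independent samples or the Mann-Whitney U-test, depending on the distribution". No Welch version, variance check or other allowance for unequal variances appears anywhere.
- **Level.** "A significance level of 0.05 will be considered, along with a corresponding 95% confidence interval".
- **Groups.** The analysis text does not say which groups are compared. The only patient classification the protocol defines is full stomach: solid or thick liquid content on ultrasound, or a volume above 1.5 mL/kg.
- **Size.** An expected prevalence of 17%, a precision of 5% and 95% confidence "resulted in a total of 217 patients to be recruited". Then: "Accounting for a 10% loss, a final total of 242 patients will be included".
- **Other analyses.** "For association analysis, univariate and multivariate linear or logistic regressions will be conducted, as appropriate".

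**The concern.** Student's t-test ordinarily means the pooled-variance test, which assumes that both groups have the same SD. When group sizes are similar, breaking that assumption does little harm. When they are very unequal, the pooled SD comes mostly from the larger group, so the standard error of the mean difference is wrong whenever the smaller group's SD differs.

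If the smaller group is more variable, p-values are too small and 95% confidence intervals too narrow. If it is less variable, the test is too conservative and real differences are easier to miss. The planning figures point to a split of nearly 5 to 1, where the pooled test is sensitive to this. The plan's only alternative, Mann-Whitney, is triggered by the shape of the distribution and not by unequal spread.

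**Working it through.** **1. The plan's own sample size.** With p = 0.17, half-width d = 0.05 and z = 1.96:

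n = z² × p(1 − p) / d² = 1.96² × 0.17 × 0.83 / 0.05² = 216.8, so 217. Allowing for 10% loss, 217 / 0.9 = 241.1, so 242. Both stated figures reproduce.

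**2. Implied group sizes.** Assume that the 17% is the proportion with a full stomach and that the groups are full versus not full: 217 × 0.17 = 36.9, about 37, leaving 180.

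**3. True error of the pooled test.** Let n₁ = 37 with SD s₁, and n₂ = 180 with SD s₂.

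- True variance of the mean difference: V = s₁²/n₁ + s₂²/n₂
- What the pooled test estimates, on average: Vp = [((n₁ − 1)s₁² + (n₂ − 1)s₂²) / (n₁ + n₂ − 2)] × (1/n₁ + 1/n₂)
- Large-sample two-sided error: 2 × [1 − Φ(1.96 × √(Vp/V))]

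The plan does not state sidedness; two-sided is assumed, in line with its 95% interval.

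*Smaller group 1.5 times as variable (s₁ = 1.5, s₂ = 1):*
- V = 2.25/37 + 1/180 = 0.0664
- Pooled variance = (36 × 2.25 + 179) / 215 = 1.209; Vp = 1.209 × 0.03258 = 0.0394
- √(Vp/V) = 0.771; error = 2 × [1 − Φ(1.96 × 0.771)] = 13.1%

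*Larger group 1.5 times as variable (s₁ = 1, s₂ = 1.5):*
- V = 1/37 + 2.25/180 = 0.0395
- Pooled variance = (36 + 179 × 2.25) / 215 = 2.041; Vp = 2.041 × 0.03258 = 0.0665
- √(Vp/V) = 1.297; error = 1.1%

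**4. Range over assumed SD ratios, 37 vs 180, nominal 5%.**

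| SD difference | Smaller group less variable | Smaller group more variable |
|---|---|---|
| none | 5.0% | 5.0% |
| 1.25-fold | 2.3% | 9.1% |
| 1.5-fold | 1.1% | 13.1% |
| 2-fold | 0.3% | 19.8% |

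Simulation of normal data with equal means (200,000 data sets per setting) agreed with these to within about 0.2 points. Welch's test on the same kind of data stayed between 4.9% and 5.2%.

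**5. Dependence on the split (1.5-fold difference, simulated).** At 72 vs 145 the pooled test gives 2.6% or 8.4%; at 108 vs 109 it gives 5.0% or 5.1%. With all 242 patients (242 × 0.17 = 41.1, so 41 vs 201) it gives 1.1% or 13.2%. The problem needs both imbalance and unequal SDs.

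**6. Mann-Whitney.** At 37 vs 180 with normal data, equal means and a 1.5-fold SD difference, its simulated error was 2.2% or 8.7%, so it does not restore the 5% level.

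**7. Cost of Welch.** For a 0.5 SD difference with equal SDs at 37 vs 180, simulated power is 78.8% for Student and 77.5% for Welch, a loss of 1.3 points.

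**The case against.** The strongest reply is that the headline rests on three things the documents do not state: the groups compared, what the 17% is a prevalence of, and the SD ratio. Surgical pathology, severity or type of anesthesia could also define groups, and with balanced groups the effect vanishes. The possible error runs from 5.0%, no problem, to 19.8%, and the documents cannot place the study within that range. The comment would also apply to many plans that name Student's test.

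Its reach may be narrow too. Many recorded items are categorical, qSOFA is a score, and fasting hours and gastric volume may be skewed enough to go to Mann-Whitney. Regression is planned alongside, and logistic regression with full stomach as the outcome does not assume equal predictor variances. Nor would the change repair the Mann-Whitney branch.

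Most of this stands as a limit on importance. It does not rescue the choice of test. Equal SDs are no better supported by the documents than unequal ones, and the group-comparison p-values and intervals will be reported whether or not regressions are also run. Where the regression is a univariate linear one on a two-level group, it is the pooled t-test under another name and carries the same assumption. Full versus not-full stomach is the only classification the protocol defines, so it is the natural reading.

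**Conclusion.** The concern holds, as a low-cost improvement. For an approximately normal variable compared between about 37 and 180 patients, the planned test's 5% error would be 2.3% or 9.1% under a 1.25-fold SD difference and 1.1% or 13.1% under a 1.5-fold difference. In the last case a nominal 95% interval would cover 100 − 13.1 = 86.9% of the time. If the SDs are equal, there is no problem.

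These sizes rest on the full versus not-full grouping, on reading the 17% as the full-stomach prevalence, and on assumed SD ratios; they illustrate the risk and do not predict it. Only secondary comparisons are affected. The prevalence estimate and the 217 and 242 figures do not depend on the t-test.

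**What to change.** In the group-comparison sentence, replace Student's test with Welch's unequal-variance t-test for approximately normal variables, and report the mean difference with its Welch 95% confidence interval. Naming the groups in the same sentence (for example, full versus not-full stomach) would let readers see the imbalance.

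The cost is one sentence of analysis text, with no added patients or data, and about 1 point of power when variances are equal. The Mann-Whitney option can remain for clearly non-normal variables, but should not be presented as the remedy for unequal spread.

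### If the 17% is full stomach, about 37 events are expected, and Firth penalisation would be a cheap improvement on default maximum likelihood for the multivariable logistic models

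*Combined protocol and SAP*

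**What the plan says.** The Research Protocol is one unnumbered text. On sample size it states: "The sample size calculation used the method for estimating a proportion". The anticipated figure is given as "A prevalence of 17% based on previous pilot studies(9"; the sentence does not say what condition the 17% describes. The result is 217 patients, raised to 242 for a 10% loss.

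Full stomach is the only gastric-content class that the protocol defines, in two parts: "If solid or thick liquid gastric content is observed, patients will be immediately classified as having a full stomach" and "Volumes greater than 1.5 mL/kg will be considered as a full stomach".

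For associations the whole specification is: "For association analysis, univariate and multivariate linear or logistic regressions will be conducted, as appropriate". No dependent variable, covariate list, limit on model size, or handling of separation is given. The data to be recorded include "Patient demographic data, surgical pathology and severity, comorbidities, fasting hours, measured gastric content, type of anesthesia, qSOFA score", but these are not declared as model terms. The only small-sample method named is for categorical comparisons: "Differences will be analyzed using Fisher's exact test or the Chi-square test". The plan asks for 95% confidence intervals without naming a type.

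**The concern.** The number of patients was chosen to estimate one proportion, and the regressions are built on whatever events that yields. With a few dozen events, maximum-likelihood logistic regression has two known weaknesses. Its log odds ratios are biased away from zero, increasingly so as parameters are added. And a binary covariate whose carriers include no event has no finite coefficient.

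The first would place adjusted odds ratios for full stomach somewhat too far from 1. The second would leave an adjusted odds ratio unreportable for an uncommon comorbidity. Nothing in the plan rules out either, and a remedy chosen after separation has appeared would be a data-driven choice.

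**Working it through.** **1. The plan's own figures.** With p = 0.17 and a half-width of 0.05: n = 1.96² × 0.17 × 0.83 / 0.05² = 216.8, so 217. For loss: 217 / 0.90 = 241.1, so 242. Both reproduce. (Reading 5% as the full width would need 868, so half-width is the reading used.)

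**2. Expected events, if the 17% is full stomach.** 217 × 0.17 = 36.9; 242 × 0.17 = 41.1. At 20, 10 and 5 events per parameter, 36.9 events support 1.8, 3.7 and 7.4 parameters (2.1, 4.1 and 8.2 at 242). These ratios are conventions and are not in the documents.

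**3. Bias and finiteness, by simulation.** The assumed inputs are: N = 217; 17% events; one true odds ratio of 2.0 per SD; other predictors null; about half the predictors binary (2, 5 and 7 binaries); 4,000 datasets per setting. Binaries have 15% prevalence except in the last row. Bias, RMSE and coverage for maximum likelihood (ML) use converged fits only.

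| | 4 parameters | 10 | 15 |
|---|---|---|---|
| ML inflation of log OR | 3.8% | 8.7% | 12.5% |
| ML odds ratio (true 2.00) | 2.05 | 2.12 | 2.18 |
| ML bias as share of 95% CI width | 3% | 7% | 10% |
| RMSE, ML | 0.216 | 0.239 | 0.264 |
| RMSE, Firth | 0.205 | 0.210 | 0.219 |
| Coverage, ML Wald | 94.9% | 94.0% | 93.4% |
| Coverage, Firth profile | 94.8% | 95.0% | 95.1% |
| ML not finite, binaries at 15% | 0.8% | 1.8% | 2.7% |
| ML not finite, binaries at 8% | 10% | 23% | 30% |

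Example of the third row, 10 parameters: 0.087 × 0.693 / 0.857 = 7%. Firth bias was within 0.3%, and Firth converged in every run. At N = 242 the ML inflation is 3.8%, 7.6% and 10.5%. Repeat runs ranged over 3–5% with 4 parameters and 8–16% with 10–15, so the tabulated values are central figures and not bounds.

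A separate simulation used other covariate sets (odds ratio 2 for every covariate, 1,000 datasets). With 3, 8 and 12 covariates the bias of the first log odds ratio was +5.5%, +9.1% and +12.1% for ML, and +1.6%, +0.3% and −0.9% for Firth.

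**4. Chance of an empty cell for one comorbidity.** With carrier risk r and prevalence q, both assumed, P(no full stomach among carriers) = (1 − r·q)^217.

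| Carrier risk | q = 15% | q = 8% | q = 5% |
|---|---|---|---|
| 17% | 0.4% | 5.1% | 15.7% |
| 30% | 0.0% | 0.5% | 3.8% |
| 10% | 3.8% | 17.5% | 33.7% |

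This accounts for the last row of the simulation table: 1 − (1 − 0.051)^k gives 10%, 23% and 31% for k = 2, 5 and 7. Those failures are essentially fits in which at least one rare binary has an empty cell.

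**5. A univariate worked case.** Suppose 0 of 17 carriers and 37 of 200 others have a full stomach.
- ML gives an odds ratio of 0 and no Wald interval.
- Fisher's exact test gives p = 0.084. The exact conditional 95% interval is 0 to 1.13. Its upper limit is the odds ratio at which the conditional probability of zero events among carriers falls to 0.025; at an odds ratio of 1 that probability is 0.036, so 1 lies inside.
- Univariate Firth gives (0.5 × 163.5) / (17.5 × 37.5) = 0.12, with a profile interval of 0.001 to 0.95 and a penalised likelihood-ratio p of 0.043. It excludes 1 beside a non-significant Fisher test.

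For a two-by-two table the exact interval is therefore the better companion to the planned test.

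**6. Side effect of Firth.** With 4 covariates and equal leverages, the average predicted risk moves from 17.0% to (36.9 + 2.5) / (217 + 5) = 17.7%.

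**The case against.** The strongest case against is that every input that makes the problem large is assumed. The documents give no regression outcome, model size or comorbidity prevalence, and gastric content might be modelled linearly instead. With about 4 common covariates the odds ratio is 2.05 instead of 2.00 and coverage is 94.9%. Even at 15 parameters ML coverage is 93.4%, and that comparison mixes estimator with interval type. Shortening the model from 15 to 4 parameters cuts the inflation from 12.5% to 3.8% with no new estimator. All of this stands, and it limits the point to a suggestion.

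It does not remove the point. The plan does not commit to a short model, and a short model does not fill an empty cell. The phrase on appropriateness in the regression sentence most naturally governs the choice between linear and logistic models, not sparse data.

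A reader might infer three stronger things, none of which the documents support:
- **That univariate results lose their interval.** The plan never specifies Wald intervals, and an exact interval that accompanies the planned Fisher test is available.
- **That up to 30% of models would be unusable.** That figure assumes seven binaries at 8% prevalence. Generally only the affected coefficient diverges.
- **That the recorded variables are the model, so 10–15 parameters are planned.** They are a data-collection list only.

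**Conclusion.** The point holds as a modest, conditional improvement. It rests on three assumptions: the 17% is full stomach, full stomach is the outcome of a multivariable logistic regression, and the model is fairly large or contains uncommon binary covariates. Under these, Firth is better than default maximum likelihood on bias, RMSE and finiteness, with little difference in coverage. With about 4 common covariates the gain is small.

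The plan contains no wrong method or contradiction here. Nor does the point imply that the sample size is inadequate: the prevalence estimate, the only quantity the study was sized for, does not depend on how the regressions are fitted.

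**What to change.** Add to the analysis text, in substance: where full stomach is the outcome of a multivariable logistic regression, the model will be fitted by Firth-penalised likelihood with profile-likelihood 95% intervals. For univariate two-by-two comparisons, Fisher's exact test is kept as planned and, where a cell is zero or sparse, the matching exact conditional interval is reported. Obtaining that interval by inverting the same two-sided test guarantees that it agrees with the p-value. Leave the linear regression, group comparisons and prevalence estimate as they are.

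The cost is one or two sentences. Standard software fits these models, and no extra patients or data are needed. The limits should be accepted knowingly: Firth adds no information, does not address covariate selection or multiplicity, and shifts predicted risks slightly toward 50%, so any predicted risks would need a re-estimated intercept (the plan mentions associations only). Naming what the 17% refers to, the regression outcome and a short covariate list would complement this change and would itself remove much of the bias.
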